2.3.1 Nonclinical Studies

The specificity of RX-0201-mediated effect on AKT-1 mRNA levels was examined in human renal cell carcinoma (von Hippel-Lindau protein-deficient renal cell carcinoma cell line) UMRC2 cells. The treatment of UMRC2 cells with RX-0201 at concentrations of 0.1 - 0.3 μ M resulted in almost complete reduction of AKT-1 mRNA levels. *In vitro* pharmacology studies have demonstrated that RX-0201 suppressed cell proliferation of human cancer cells of various origins, including pancreatic cells. RX-0201 was evaluated for antitumor activity in athymic nude mice implanted with fragments of human tumors, which included PANC-1 pancreatic carcinoma cell line. While no significant antitumor effects were observed in PANC-1, treatment with RX-0201 did appear to result in increased survival benefits at the dose levels tested.

When treated with RX-0201 no significant effects were seen in acute toxicity studies in Cynomolgus monkeys and Sprague-Dawley rats. Possible RX-0201 related effects in 14-day toxicity studies in Cynomolgus monkeys included decreased red blood cells and histological findings in the liver, kidneys, and lymphatic tissues. Possible RX-0201 related effects in 14-day toxicity studies with Sprague-Dawley rats include: lower red blood cell parameters seen in all treated groups that persisted through the recovery period, as well as changes in kidney and liver histology and other hematologic and blood chemistry parameters.

The effect of RX-0201 when given in combination with everolimus on renal cancer cell proliferation was studied in Caki-1 and UMRC2 cells. An additive effect on growth inhibition was observed when either Caki-1 or UMRC2 cells were treated with a combination of RX-0201 and everolimus. These results suggest that when RX-0201, when combined with everolimus, may increase inhibition of cell proliferation.

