9.5.2.2 Laboratory Safety Data

All hematology, chemistry, coagulation and urinalysis will be listed by treatment group and subject. Where normal ranges are available, values outside of the range will be flagged. The data will be summarized by treatment group using standard descriptive statistics at each of the scheduled time point in the study. For continuous parameters, a summary of the changes from baseline to each post dose laboratory assessment will also be produced for each treatment group.

Shift analysis for selected laboratory parameters between baseline and both the final visit worst-case on-study value will be summarized according to NCI CTCAE version 4.03 toxicity grades.

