## Safety Analyses

The incidence of subjects with adverse events and clinical laboratory abnormalities, defined as dose limiting toxicities after 1 cycle of therapy, is one of the primary endpoints. The safety of RX-0201 will be evaluated through reporting using the grading system in the CTCAE version 4.03 for adverse events and laboratory abnormalities. This will be used to grade changes in vital signs, and laboratory assessments to include serum chemistry, hematology, coagulation tests and urinalysis. All statistical methods for safety data will be descriptive in nature.

Dose Limiting Toxicities that occur during Cycle 1 will be tabulated by DLT criteria and RX-0201 dose level. Vital signs will be tabulated and presented as raw data and change from baseline at each time point. Laboratory safety data will be tabulated in shift tables based on laboratory-specific normal ranges. Adverse events will be tabulated by body system, intensity and relationship to study drug.

Vital signs, weight, and data will be summarized using appropriate descriptive statistics, by treatment group and time.

All subjects who receive at least 1 dose of RX-0201 will be included in the final summaries and listings of safety data. All safety analyses will be performed by dose level, treatment cycle, and week, where appropriate.

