### **8.13 Clinical Laboratory Evaluations**

Abnormal laboratory values will be assessed according to NCI CTCAE v4.03 where possible. The criteria for “clinically significant” laboratory abnormalities include a laboratory abnormality that leads to a DLT or a laboratory abnormality that results in any treatment-emergent therapeutic intervention (i.e., concomitant medication or therapy), or any other laboratory abnormality judged by the investigator to be of other particular clinical relevance.

All relevant clinical laboratory tests will be classified as Low, Normal, and High, or Normal/Abnormal according to the normal ranges. This categorical data will be summarized in shift tables comparing the results at each scheduled post-baseline visit with those at the baseline visit.

When there are multiple values within a visit for a particular laboratory variable, the worst value will be taken (worst being the smallest value for criteria below a certain threshold or the largest value for criteria above a certain threshold). If a subject has both a value below the threshold and a value above the threshold, the value furthest from the threshold will be chosen.

Urinalysis data will be presented in subject listings only.

All laboratory (hematology, coagulation, clinical chemistry, and urinalysis) parameters, values, units, normal range, flags collected (normal/abnormal) in the clinical database will be included in by-subject listings for further medical review. Laboratory values with associated CTCAE version 4 grades will have the associated grade displayed.

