## **11 Summary of Changes to the Protocol**

None.

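### SAP 8.13 confines urinalysis to subject listings, an undeclared departure from the protocol's planned summary by group and time point, so urine changes not reported as AEs or DLTs reach no table

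*SAP*

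**What the plan says.** Protocol 9.5.2.2 opens with all four panels: "All hematology, chemistry, coagulation and urinalysis will be listed by treatment group and subject". It then adds: "The data will be summarized by treatment group using standard descriptive statistics at each of the scheduled time point in the study". For continuous parameters it also plans a summary of change from baseline at each post-dose assessment. Its shift analysis is narrower: "Shift analysis for selected laboratory parameters between baseline and both the final visit worst-case on-study value". Protocol 9.5.1 sets counts and percentages as the form for categorical data and requires the SAP to describe any change from the protocol's analyses.

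SAP 8.13 classifies laboratory tests and shows them as shifts from baseline at each post-baseline visit: "All relevant clinical laboratory tests will be classified as Low, Normal, and High, or Normal/Abnormal according to the normal ranges". It then takes one panel out: "Urinalysis data will be presented in subject listings only". The unnumbered SAP section Safety Analyses, which follows 8.6, includes urinalysis in what is to be graded: "laboratory assessments to include serum chemistry, hematology, coagulation tests and urinalysis". The same section puts laboratory safety data into shift tables and makes no exception for urinalysis. SAP 11, "Summary of Changes to the Protocol", has a one-word entry saying that there are none.

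**The concern.** Change in clinical laboratory tests over time is a secondary endpoint in both stages (Protocol 9.2.1.2; SAP 4.2 and 8.8). One of the four panels that feed it is collected throughout treatment but gets no count, percentage or change by group. Readers of the study report would have to find any pattern themselves in by-subject listings.

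Urine is a reasonable place to look. Protocol 2.3.1 lists kidney histology findings among the possible RX-0201 effects in 14-day monkey studies, and for rats it reports "changes in kidney and liver histology and other hematologic and blood chemistry parameters". Fourteen days is also the length of each infusion period in this trial. The urinalysis panel includes protein and hemoglobin.

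**Working it through.** The plan gives no figure to reproduce, so the check compares the texts and then traces what is left untabulated.

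**Step 1: protocol against SAP.** In 9.5.2.2 the sentence on descriptive summaries follows directly on the one naming the four panels and excludes none of them. Urinalysis is therefore within the planned summary. Because shifts are promised only for selected parameters, the protocol does not guarantee urinalysis a shift table. What it guarantees is a descriptive summary by group and time point, and for categorical results that means counts and percentages. SAP 8.13 removes it.

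**Step 2: SAP against itself.** That urinalysis is to be graded does not in itself conflict with listings, since 8.13 displays CTCAE grades there. The conflict is with the statement in Safety Analyses that laboratory safety data go into shift tables, without exception.

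**Step 3: declaration.** If 8.13 governs, the SAP departs from the protocol while Section 11 reports no change. If Safety Analyses governs, the sentence in 8.13 is an error. The text needs correcting on either reading.

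**Step 4: what still reaches a table.**

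| Urine or renal finding | Where it appears under the SAP |
|---|---|
| Urine abnormality that needs intervention or further investigation, or leads to interruption or discontinuation of drug | It is an AE unless tied to a clinical event already reported (Protocol 8.1.1; SAP 8.10), and so in the treatment-emergent AE tables |
| RX-0201-related non-hematological toxicity of Grade 3 or higher in Cycle 1 | DLT table (SAP 5.5.1 and Safety Analyses) |
| Serum creatinine, BUN | Chemistry shift tables (Protocol Appendix C; SAP 8.13) |
| Urine change below the AE threshold | Listings only |

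Only the last row is lost. SAP 8.10 leaves such changes to general laboratory monitoring, which for urinalysis now means the listings.

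**Step 5: amount of data.** Appendix C of the protocol lists 11 urinalysis analytes. Samples are taken at screening, before each cycle (Cycles 1 to 16 in Stage 2) and at end of treatment.

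- Full 8 cycles: 1 + 8 + 1 = 10 per subject, or 9 if screening tests within 72 hours replace Cycle 1 Day 1.
- For 20 Stage 2 combination subjects: 9 × 20 = 180 to 10 × 20 = 200.

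This count is illustrative; it is neither an estimate nor a bound. Subjects may stop early: eight cycles are 8 × 21 = 168 days, or 168 / 30.44 = 5.5 months, and with the protocol's expected 9-month median PFS and exponential progression (my assumption), 0.5^(5.5/9) ≈ 0.65 would still be progression-free then. Others may continue past 8 cycles.

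The documents give no rate of new urine abnormality. At an assumed 5% to 25%, 0.05 × 20 = 1 to 0.25 × 20 = 5 subjects would be affected, and only those below the AE threshold would be confined to listings.

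**Step 6: continuous laboratory values.** SAP 7.3.5 gives N, mean, SD, median and range for safety measures in general. Safety Analyses specifies change from baseline for vital signs. Neither it nor 8.13 does so for laboratory values, although Protocol 9.5.2.2 plans it.

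**The case against.** The best defence is that 8.13 is the more specific text and so controls, that Protocol 9.5.1 lets the SAP change an analysis, and that little is lost: about 23 Stage 2 subjects, an open-label design, flags and grades in the listings, and no efficacy or dose decision that turns on urinalysis. Much of this stands. The SAP may change the analysis, and material events are tabulated elsewhere. But the sentence in 8.13 is not presented as a change, no reason is given, and Section 11 says there are none. Specificity also does not remove the contrary statement in Safety Analyses.

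A reader might infer that a renal signal would appear in no table. The documents do not support that, because the AE, DLT and chemistry tables all remain. A reader might also take the animal data as evidence of a urine effect. Protocol 2.3.1 reports histology, calls it a possible effect, and mentions no urine finding in either species.

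On the lesser point, it would be too strong to say that laboratory data get shift tables only, given the general descriptive statistics in SAP 7.3.5. The explicit change-from-baseline summary is nonetheless missing.

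**Conclusion.** The point holds in limited form. SAP 8.13 drops a summary that Protocol 9.5.2.2 plans, disagrees with the SAP's Safety Analyses text, and is not declared in SAP 11. As a result, urinalysis appears in no laboratory summary or shift table, and low-grade or asymptomatic urine changes not reported as AEs or DLTs are visible only in by-subject listings. Renal safety reporting as a whole is not lost. The conclusion rests on reading the protocol's summary sentence as covering all four panels just named, which is its plain sense. The sample count and the assumed rates show scale only, and the conclusion does not depend on them. The missing change-from-baseline summary is a lesser gap of the same kind. It is worth correcting because it affects a secondary safety endpoint and is cheap to fix. It is a matter of reporting and does not touch clinical management.

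**What to change.** In SAP 8.13, delete the listings-only sentence. State instead that urinalysis parameters, at least protein and hemoglobin, will be summarised by treatment group and scheduled visit, either as counts and percentages or as a Normal/Abnormal shift from baseline. The shift form by visit agrees with Safety Analyses as it stands; if plain counts are chosen, add a matching exception there. If some urinalysis parameters are left untabulated, declare and justify that in Section 11.

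Also add to 8.13 the protocol's summary of change from baseline by treatment group for continuous laboratory parameters.

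More elaborate urine tables, such as worst post-baseline category or CTCAE grade, go beyond what the protocol promises and are optional. The cost is SAP wording and one or two tables, with no new data collection.

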### **8.14 Other Safety Measures**

#### **8.14.1 ECOG Performance Status**

ECOG performance status results will be summarized descriptively using N frequency and percentage by dose group at each visit.

### **8.14.2 Vital Signs**

Resting vital signs, including pulse, blood pressure, respiration rate, temperature and weight, will be collected at screening, days 1, 8 and 15 of each cycle, end of treatment (or early termination), and safety follow-up visits. They will be summarized descriptively as will change from baseline results by treatment group and assessment time point.

## **9 Efficacy Analyses**

### **9.1 Primary Efficacy Analysis**

Tumor assessment(s) will be performed by the investigator using RECIST Version 1.1 criteria with modifications (Appendix E of the protocol) at the end of every 2 cycles

Subjects first meeting criteria for complete response or partial response at the last on-treatment tumor assessment should have a follow-up tumor assessment at the End of treatment or Early Termination visit providing it is  $\geq 3$  weeks from the previous tumor assessment.

The results will be available before the beginning of the next cycle. Radiographic tumor assessment(s) performed during the screening period will be used to prospectively identify all sites of disease present at the start of treatment. Subjects with symptoms suggestive of disease progression will be evaluated for tumor progression at the time symptoms occur.

The efficacy endpoints analyzed for this study are tumor response (complete response (CR) plus partial response (PR) according to RECIST), progression-free survival (PFS), time to response and response duration (for responders only). Progression-free survival is defined as time from first dose to the earlier of either first documented disease progression or death from any cause. Time to response is defined as time from first dose to first PR or CR (that is subsequently confirmed). Duration of response will be defined as time from first PR or CR (that is subsequently confirmed) to the earlier of either first documented disease progression or death from any cause.

#### **9.1.1 Progression-Free Survival**

Progression-free survival (PFS) will be defined as the date treatment starts to the date of first documented disease progression (PD) or death due to any cause, whichever comes first. Subjects alive without disease progression or lost to follow up at the time of analysis will be censored at the date of last response assessment. Table 1 below shows the censoring rules for progression-free survival.

The distribution of the progression-free survival will be estimated and graphed using Kaplan-Meier method. If applicable, estimates of the 25th percentile, median and 75th percentile and their respective 95% confidence intervals will be provided.

Kaplan-Meier curves for RX-0201 in combination with everolimus and everolimus alone will be estimated separately but displayed on one graph as a visual comparison of the survival curves between treatment groups. The log-rank test will be performed to compare the survival curves at the 0.05 significance level.

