1. OBJECTIVES

1.1 Primary

- To determine the maximum tolerated dose (MTD) of RX-0201, up to a target dose of 250 mg/m²/day, when given in combination with everolimus (Stage 1)
- To determine progression free survival in subjects with advanced renal cell carcinoma treated with the combination of RX-0201 and everolimus versus everolimus alone (Stage 2)

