3. EXPERIMENTAL PLAN

3.1 Study Design

The current study will be a phase 1b/2, multicenter, open label study conducted in 2 stages. Stage 1 will be an open-label, dose-escalation phase 1b study of RX-0201 administered in combination with everolimus. It is expected that 250 mg/m²/day or a lower dose of RX-0201 will be identified as safe and well-tolerated when administered in combination with everolimus. The initial dose of RX-0201 will be 125 mg/m²/day. RX-0201 will be administered by continuous intravenous infusion for 14 days followed by 1 week of rest. The dose of RX-0201 identified in Stage 1 will be studied further in the dose expansion portion (Stage 2). In Stage 1 and Stage 2, everolimus (10 mg) will be administered daily according to the approved label instructions.

Stage 2 will be an open-label, 2-arm phase 2 study of RX-0201 in combination with everolimus versus everolimus alone. Subjects will receive either RX-0201, at the dose identified in Stage 1, in combination with everolimus for up to 8 cycles until withdrawal of consent, pregnancy, substantial noncompliance with study procedures, intolerable adverse event, documented radiological disease progression (per RECIST ver. 1.1 see Appendix E), death, principal investigator judgment that it is in the best interest of the subject to stop treatment, or study discontinuation. For subjects receiving RX-0201 and everolimus therapy and, in the opinion of the investigator, is receiving benefit after 8 cycles, additional cycles of RX-0201 plus everolimus may be administered following discussions with the Sponsor. Prior to this amendment, subjects were randomized to receive everolimus alone. Subjects randomized to the everolimus only treatment arm will complete the study after 8 cycles but may continue to receive everolimus off-study.

The study endpoints are defined in Section 9.2.

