9. STATISTICAL CONSIDERATIONS

9.1 Study Design

9.1.1 Stage 1

Stage 1 is a dose escalation study to determine the MTD up to a target dose of 250 mg/m²/day of RX-0201 in combination with everolimus. The starting dose of RX-0201 will be 125 mg/m²/day. The secondary objectives of Stage 1 of the study are described in Section 1.2.

9.1.2 Stage 2

Prior to starting Stage 2, the principal investigators, medical monitor and sponsor will review the safety, laboratory and dosing information to make decisions regarding the start of Stage 2. Approximately 20 additional subjects will be treated with the combination of everolimus and RX-0201. The primary objective of Stage 2 is to determine progression free survival. The primary analysis will be conducted approximately 6 months after the last enrolled subject is treated. The secondary objectives of Stage 2 of the study are described in Section 1.2.

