9.3 Sample Size Considerations

Approximately 9 subjects will be enrolled in Stage 1 of the study. Stage 1 is designed to determine the MTD up to a target dose of 250 mg/m²/day of RX-0201, thus the sample size for the study is not based on a formal statistical hypothesis but will be determined based on observed number of first-cycle DLTs at each dose level. The sequential 3+3 dose-escalation is

consistent with usual oncologic paradigms for dose ranging as the intent is to limit the number of subjects who are exposed to toxic doses of the treatment combination. The trial will use the standard National Cancer Institute (NCI) definition of MTD (starting dose associated with DLT in < 33.3% of subjects during the first cycle of therapy).

The planned sample size for Stage 2 is approximately 10 subjects in the everolimus arm and 20 subjects in the everolimus/ RX-0201 arm. The primary goal is to provide preliminary estimates of safety and efficacy endpoints when combining everolimus and RX-0201. Safety endpoints will be reported as described in Section 8. The primary efficacy endpoint is progression free survival estimated using the Kaplan-Meier method and associated 90% confidence intervals. Median PFS is expected to be 4.5 months in the everolimus only arm and 9 months in the combination arm. With 10 evaluable subjects in the everolimus only arm the width of the two-sided 90% confidence interval for 9-month PFS will be no more than ± 0.28 . With 20 evaluable subjects in the combination arm the width of the two-sided 90% confidence interval for 9-month PFS will be no more than ± 0.20 .

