9.5.2.3 Time to Event Analyses

The detailed statistical analysis methods for each endpoint will be described in the statistical Analysis Plan (SAP). The Kaplan-Meier method will be applied to the following time to event endpoints:

- Progression-Free Survival: The time from first study dose to the first observation of disease progression (as classified by RECIST ver. 1.1) or death due to any cause.
- Time to response: The time from first study dose to the first observation of a complete or partial tumor response that is subsequently confirmed.
- Duration of response: The time from the first observation of a complete response or partial tumor response (whichever comes first) to the subsequent time of disease progression or death (whichever comes first) will be calculated as the duration of response for each subject.

Kaplan-Meier estimates and 2-sided 95% confidence interval for landmark times by 6-week intervals will be produced for the endpoint of progression-free survival time. Descriptive statistics for the duration and time to response for the responding subjects will be calculated.

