## **7 General Considerations**

The software used for all summary statistics and statistical analyses will be SAS Version 9.4 or later.

Safety, Efficacy, and PK assessments will be summarized separately for Stage 1 and Stage 2.

Additional summaries and analyses of pooled Phase 1 and 2 data may also be generated based on applicability of dosing regimens.

Unless otherwise noted, data will be summarized in tabular format by increasing dose level of RX-0201 for the combination of RX-0201 and Everolimus in Stage 1, by combination of RX-0201 and Everolimus in Stage 2, and by RX-0201 dose level for the combination of RX-0201 and Everolimus Stage 2. All groups combined (i.e., Total/Overall column) will also be presented when appropriate. All study data documented on the eCRFs will be included in the study data listings.

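### SAP 9.1.1 keeps an exploratory 0.05 log-rank test of up to 20 combination subjects against about 3 everolimus subjects, and Protocol 9.3 keeps sample-size figures for a control arm that has been removed

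*SAP*

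**What the plan says.** Protocol 2.3.2 explains that the everolimus-alone arm and randomisation are removed by the current amendment. Protocol 5.3 and SAP 5.4 assign all further Stage 2 subjects to the combination. Protocol 3.3 and SAP 6 put Stage 2 at about 3 everolimus-alone and up to 20 combination subjects.

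Other text still describes the two-arm trial:

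- **Test.** SAP 9.1.1 overlays the two PFS curves and adds: "The log-rank test will be performed to compare the survival curves at the 0.05 significance level". SAP 9.1.3 asks for a log-rank test on time to response but names only the combination curve.
- **Sample size.** Protocol 9.3 states: "The planned sample size for Stage 2 is approximately 10 subjects in the everolimus arm and 20 subjects" in the combination arm. It adds 90% interval half-widths for 9-month PFS of no more than ±0.28 (10 subjects) and ±0.20 (20 subjects).
- **Objective.** Protocol 1.1 and SAP 4.1 define the Stage 2 primary objective in subjects "treated with the combination of RX-0201 and everolimus versus everolimus alone (Stage 2"). Protocol 9.1.2 has no comparator: "The primary objective of Stage 2 is to determine progression free survival". The synopsis, under Statistical Considerations, has none either.
- **Design.** The protocol synopsis, Protocol 3.1 and SAP 5.1 still call Stage 2 a two-arm study.

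The protocol's own analysis is estimation. Section 9.3 says: "The primary goal is to provide preliminary estimates of safety and efficacy endpoints when combining everolimus and RX-0201". Section 9.5.2.3 says: "Kaplan-Meier estimates and 2-sided 95% confidence interval for landmark times by 6-week intervals will be produced". On control follow-up, Protocol 3.1 says: "Subjects randomized to the everolimus only treatment arm will complete the study after 8 cycles but may continue to receive everolimus off-study".

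**The concern.** A significance test under the primary efficacy heading invites a reader to treat its result as evidence about RX-0201. With about 3 controls, a non-significant result says almost nothing. A significant one would turn on the timing of one or two control events in a comparison that is mostly not randomised.

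The sample-size section has a separate fault. It is the only quantitative justification for Stage 2, and its control-arm half describes subjects who will not be enrolled and a time point the existing controls do not reach. It also gives precision at 9 months, whereas the Stage 2 primary endpoint (Protocol 9.2.1.1, SAP 4.2) is PFS at 4.5 months.

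**Working it through.** **Inputs.** Medians 4.5 and 9 months (Protocol 9.3); 3 v 20 subjects (Protocol 3.3, SAP 6); two-sided 5% (SAP 7.3.5); controls leave after 8 cycles of 21 days (Protocol 3.1); scans every 6 weeks (Protocol 7.6). Assumptions: exponential PFS, no dropout, scans on schedule. The documents state no power and no event target.

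**1. Reproduce the plan's figures.** The largest half-width of an exact (Clopper-Pearson) 90% interval over all outcomes is 0.278 for n = 10 and 0.198 for n = 20. These match ±0.28 and ±0.20, so the arithmetic was right for 10 v 20.

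**2. Same method with 3 controls.** The largest half-width is 0.424. With 2 of 3 progression-free, the 90% interval runs from 0.14 to 0.98.

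**3. Control follow-up.** 8 × 21 = 168 days = 24 weeks = 5.5 months. Nine months is 9 × 30.44 = 274 days. Reaching it would need 274 − 168 = 106 days of delay, about 13 days in every one of the 8 cycles.

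**4. Power by Schoenfeld's formula.** HR = 4.5/9 = 0.5 and p = 3/23, so p(1 − p) = 60/529 = 0.1134.

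Power = Φ(ln 2 × √(0.1134 d) − 1.96), where d is the number of events.

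- Events expected by 5.5 months: 20(1 − 0.5^(5.5/9)) + 3(1 − 0.5^(5.5/4.5)) = 6.9 + 1.7 = 8.6. Power = Φ(0.685 − 1.96) = 10%.
- All 23 subjects with an event (the ceiling): Φ(1.120 − 1.96) = 20%.
- For scale, 80% power needs (1.960 + 0.842)² / (0.1134 × 0.4805) ≈ 144 events.

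**5. Power by simulation.** With 3 v 20, times rounded up to 6-weekly scans, controls censored at 24 weeks and a cut-off of 3.84, power is 18%. The mean number of control events is 1.7 and rejection under the null is 5-6%. Longer combination follow-up leaves this unchanged, because no control is at risk after week 24 and later events add nothing to the statistic. If controls were instead followed until progression, simulated rejection would be 26-27%, but null rejection would be about 9%, so that figure overstates usable power.

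**6. Randomisation.** Nine Stage 2 subjects had been randomised by 06 March 2017 (Protocol 2.3.2); the split is not given. If all 3 controls are among them, 9 − 3 = 6 combination subjects were randomised and up to 20 − 6 = 14 were not.

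**7. Precision the trial can offer.** A 9-month median implies 4.5-month PFS of 0.5^(4.5/9) = 0.707 on the combination. For 20 subjects all assessed to that time, the 95% log-log interval is S^exp(±1.96 √[(1 − S)/(20 S)] / |ln S|).

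- At S = 14/20: √(0.3/14) = 0.146; 1.96 × 0.146/0.357 = 0.804; limits 0.70^2.235 = 0.45 and 0.70^0.447 = 0.85.
- Across outcomes, half the total width is at most about 0.21, and the longer arm reaches about 0.25.
- The exact 95% method gives a half-width of at most 0.23; at 14/20 it gives 0.46 to 0.88.

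**The case against.** The strongest reply is that little depends on the test. SAP 7.3.5 labels every inferential test exploratory, SAP 6 says the sample size was set empirically, and no decision rule uses the p-value. Judging the test against 80% power applies a confirmatory standard the documents never adopt. Protocol 9.5.2.3 also leaves detailed methods to the SAP, so adding a test is not forbidden. All of this stands, and it limits the severity. It does not make the p-value informative, and it does not touch Protocol 9.3, which is wrong as written. SAP 11 records no changes, although Protocol 9.5.1 says that changes from its analyses will be described in the SAP.

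Two stronger readings should be resisted.

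- **That the comparison is impossible.** Some subjects were randomised, both curves can be drawn, and a log-rank statistic can be computed. SAP 7 lists Stage 2 tables only "by combination of RX-0201 and Everolimus in Stage 2", but that list applies unless otherwise noted, and SAP 9.1.1 notes otherwise.
- **That the SAP leaves the primary endpoint without an analysis.** SAP 4.3 says PFS will be analysed at 4.5 months, SAP 9.1.1 supplies Kaplan-Meier, SAP 7.3.5 supplies two-sided 95% intervals, and SAP 7.2.1 supplies a population. What is missing is detail: an explicit line in 9.1.1, the interval method, and a time origin for untreated subjects. The protocol's 6-weekly landmarks miss 4.5 months (19.6 weeks), but week 18 is close: 0.727 against 0.707 at a 9-month median.

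**Conclusion.** The point holds as a correction of text left over from the two-arm design. The log-rank test is uninformative: about 10-20% power at the protocol's assumed effect (18% by simulation with controls censored at 24 weeks), with fewer than 2 expected control events, in a comparison that is largely non-randomised and possibly non-concurrent. The power figures rest on exponential PFS, no dropout and on-time scans. The count of up to 14 non-randomised combination subjects also assumes that all 3 controls were among the first nine randomised.

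The 10 v 20 split and the ±0.28 in Protocol 9.3 do not describe the current trial, whatever is assumed about effect size. The comparative objective in Protocol 1.1 and SAP 4.1 conflicts with Protocol 9.1.2 and the synopsis statistics text. Stage 1 is unaffected, and so is estimation of combination-arm PFS at 4.5 months.

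**What to change.** 1. Delete the log-rank tests in SAP 9.1.1 and 9.1.3. Show everolimus-alone subjects descriptively.
2. In Protocol 1.1, the synopsis objectives and SAP 4.1, restate the Stage 2 primary objective as estimating PFS on RX-0201 plus everolimus.
3. In Protocol 9.3, replace 10 v 20 with the numbers in Protocol 3.3 and delete the ±0.28 statement. Give precision for 4.5-month PFS in the combination arm at one confidence level: 95%, as in Protocol 9.5.2.3 and SAP 7.3.5. Compute it by the method used for the planned interval. For 20 subjects all assessed to 4.5 months, log-log gives half the total width at most about 0.21 and a longer arm up to about 0.25 (14/20: 0.45 to 0.85). The exact method gives at most 0.23. Do not quote one method's figure beside the other's interval.
4. In SAP 9.1.1, state that the primary Stage 2 result is the Kaplan-Meier PFS estimate at 4.5 months, with its 95% interval and the interval method, in treated combination subjects. PFS starts at first dose, and Protocol 5.4 replaces untreated Stage 2 subjects. Reconcile this with the all-enrolled Full Analysis Set in SAP 7.2.1. In the SAP 9.1.1 censoring table, replace the randomisation date with the date of first dose. Align the population of the PFS plot in SAP 13, now the tumour-response evaluable set.
5. Correct the two-arm wording in the protocol synopsis, Protocol 3.1 and SAP 5.1, and record the changes in SAP 11.

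Cost: wording in both documents and no new data. The only loss is an exploratory p-value that no decision uses.
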